The clinical evidence supporting this phenomenon has grown over the past few years. The induction or exacerbation of psoriasis during anti-TNF therapy, which has now been reported in several hundred patients (9, 10) is one such example, and may occur in patients treated for inflammatory conditions other than psoriasis. The psoriatic lesions of these patients have a greatly increased type I interferon signal, as determined by increased tell-tale Myxovirus Resistance Gene A (MxA) expression, compared with control psoriasis samples and similar observations have been made in patients exposed to the Toll-like receptor (TLR)-7 agonist imiquimod. Imiquimod is a very effective inducer of type I interferon production by pDCs (15) and has been shown to exacerbate psoriasis both at the treated area as well as distant skin sites. Similarly, to anti-TNF exacerbated psoriasis, this reaction is accompanied by influx of pDCs and increased MxA expression. Interestingly, but in line with the observations above, this reaction appears to be exacerbated in patients on anti-TNF treatment. This cross-regulation is likely to extend beyond psoriasis as diseases characterized by increased type I IFN signal are frequently exacerbated or triggered by TNF treatments, including lichenoid skin reactions and the increased frequency of positive anti-double stranded DNA antibody titers and less commonly clinical systemic lupus erythematosus, which are both reversible upon discontinuation of treatment.

We have demonstrated that the inflammatory and cytokine network in chronic plaque psoriasis is heterogenous with large variation in the strength of the type I

IFN- $\alpha$  and TNF- $\alpha$  signals between different patients. Thus, about 35-40% of patients show an enriched IFN- $\alpha$  signature in lesional psoriatic skin, which, perhaps coincidentally, is around the same ratio of patients showing limited response to etanercept therapy. Our analysis of a small cohort of patients (n=15) treated with etanercept indicated that those patients with increased IFN- $\alpha$  signal had poorer response to therapy and that the strength of the IFN- $\alpha$  signal was the main predictor of treatment response.

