1. Demonstrate that the strength of type I IFN signature in psoriatic skin predicts treatment response.

Fifty individuals with moderate to severe psoriasis with high dose etanercept (50mg twice weekly), and the composition of the lesional psoriatic cytokine network will be tracked at the onset (day 0), early (week 2), during the middle (week 6) and at the end of treatment (week 12). Serum samples and PBMC isolation will be done at each time-point for later analyses. Biopsies of uninvolved and lesional skin will be performed before initiation of treatment and then lesional biopsies taken at week 2, week 6 and week 12. Skin will be anaesthetized with 1% lidocaine with epinephrine and 6mm punch biopsies will be taken. Photographs of patients will be obtained and the anatomical location of biopsies recorded. Biopsies will be bisected, with one-half snap frozen in liquid nitrogen and stored at -80° until RNA and protein processing and the other half fixed in 4% formalin for paraffin embedding and immunohistochemistry. Processing will be performed as previously described by our team and only high quality RNA, as determined by Agilent 2100 Bioanalyzer will be used .

Next-generation sequencing of RNA (RNAseq) will be performed on the samples according to Illumina's protocol using 2 $\mu$ g of RNA. Immunohistochemistry will be performed to validate findings with MXA staining used to confirm presence of type I interferon signal. H&E staining will be used to assess the degree of epidermal hyperplasia and response to treatment and immunohistochemical detection of keratin 16, CD3, CD11c, CD163, Ki67 used to validate the degree of histologic response in context of the clinical response. QRT-PCR will be performed for selected gene transcripts to validate the findings of RNAseq.

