(1) First, we will test whether temporal change in PASI score is significantly associated with baseline TNF- $\alpha$  signal, baseline IFN- $\alpha$  signal, and/or an interaction between these two baseline signals. Along these lines, a cumulative score reflecting change in PASI during the course of etanercept treatment will be calculated for each patient. This score will then be treated as a continuous response variable, and we will use robust linear modeling to test whether scores are significantly associated with baseline TNF- $\alpha$  signal, baseline IFN- $\alpha$  signal, and/or an interaction between these two signals. In addition, we expect that it will be possible to unambiguously classify 30% of patients as non-responders, with an equal percentage showing clear improvement in PASI score, and the remainder showing an intermediate response. Accordingly, we will also categorize patients according to improvement in PASI score (i.e., responders, intermediate-responders, and non-responders), and use cross-validation to calculate AUC statistics to directly quantify the capacity of baseline TNF- $\alpha$  and IFN- $\alpha$  signals to predict patient response status. Based upon preliminary data ( $n$  = 15 patients), we anticipate that improved PASI score will be associated with a heightened baseline TNF- $\alpha$  signal and weakened baseline IFN- $\alpha$  signal. The proposed study design will allow us to not only confirm this expectation, but will provide increased power to assess a possible TNF- $\alpha$ /IFN- $\alpha$  interaction effect, and to better characterize quantitative thresholds associated with response and non-response.

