(2) Second, we will test whether TNF- $\alpha$  and/or IFN- $\alpha$  signals are significantly altered during the course of etanercept therapy, and whether such changes differ between subjects with different PASI response profiles. In these analyses, TNF- $\alpha$  or IFN- $\alpha$  signal will be treated as a response variable in a univariate repeated measures analysis of variance, with subject and time as covariates. In this framework, a shift in TNF- $\alpha$  or IFN- $\alpha$  signal during the course of etanercept treatment will be indicated by a significant time effect. In follow-up analyses, models will include 0-1 covariates indicating specific PASI response profiles (e.g., non-responder, intermediate-responder, or responder), which will allow us to test whether temporal shifts in TNF- $\alpha$  or IFN- $\alpha$  signals differ according to the effectiveness of etanercept treatment (i.e., by evaluating interaction effects involving time and 0-1 covariates denoting PASI response patterns). We anticipate that etanercept treatment will more strongly attenuate TNF- $\alpha$  signals in responders compared to intermediate-responders or non-responders (possibly due to disparities in baseline TNF- $\alpha$  and IFN- $\alpha$  signals). Conversely, we expect that non-responders will be characterized by high IFN- $\alpha$  signals, which remain high during the course of etanercept treatment. All analyses performed using PASI scores will be repeated using physician global assessment scores as the response variable, although we expect results from these two analyses to be consistent. With 50 patients recruited and treated, we estimate that we will have >95% statistical power to detect significant effects in the proposed design (Type I error rate of 0.05). Although the analysis will be primarily focused on TNF and IFN signatures, this dataset will also provide us with opportunities to determine contribution of other inflammatory cellular and cytokine contribution to the clinical response.

**Anticipated Results:** We expect that patients with strong IFN- $\alpha$  signature in psoriatic skin along with weak TNF- $\alpha$  signature will have minimal response to anti-TNF treatment, while patients with the opposite pattern, weak IFN and strong TNF signature, will have significant clinical improvement.

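### The cumulative PASI score has no formula, baseline adjustment or missed-visit rule, and the >95% power for 50 treated patients names no test, effect size or allowance for losses

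*Combined protocol and SAP*

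**What the plan says.** **Outcome.** Part (1) of Analysis/Statistics states that "a cumulative score reflecting change in PASI during the course of etanercept treatment will be calculated for each patient". The score is a continuous response, and "we will use robust linear modeling to test whether scores are significantly associated with baseline" TNF signal, baseline IFN signal and their interaction. Baseline PASI is not among the covariates. The visit flow chart schedules PASI at screening, baseline and weeks 2, 6 and 12. The plan does not say whether the score is a sum or an area, whether it is on the absolute or percent scale, or how a missed visit is handled.

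**Usable samples.** Under aim 1, the sequencing description adds that "only high quality RNA, as determined by Agilent 2100 Bioanalyzer will be used". No failure rate, quality cut-off or re-biopsy rule follows.

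**Power.** Part (2) closes with "With 50 patients recruited and treated, we estimate that we will have >95% statistical power to detect significant effects in the proposed design", at a "Type I error rate of 0.05". No test is named and no effect size or standard deviation is given. The only prior data mentioned are qualitative: "Our analysis of a small cohort of patients (n=15) treated with etanercept" suggested poorer response with a stronger IFN signal. No dropout rate, replacement rule or analysis set is stated.

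**The concern.** A quantity accumulated over visits can depend on how many visits there were. If the score is added up over the visits a patient attended, two patients with the same course get different values when one leaves early, and the difference is read as a difference in response. If only completers are scored, that distortion goes but patients are discarded. The hypothesis is that patients with a high IFN signal respond poorly. If poor responders leave more often, the discarded patients are related to the predictor under test.

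On an absolute scale the score also depends on starting severity, which the model does not adjust for.

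The power statement raises a second, separate issue. The count is of patients treated. Part (1) needs a usable baseline lesional RNA sample plus follow-up PASI, and part (2) needs usable lesional RNA over time. Any loss makes the number analysed smaller than 50, and the statement gives nothing from which to judge whether that matters.

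**Working it through.** **1. How the score behaves under different definitions**

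The visit weeks (2, 6, 12) come from the plan. The PASI courses are assumed: baseline 20, with falls at weeks 2/6/12 of 20/50/75% (responder), 12/30/45% (intermediate) and 5/10/15% (non-responder). In points these are 4/10/15, 2.4/6/9 and 1/2/3.

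- Sum: responder 4 + 10 + 15 = 29; lost after week 6, 4 + 10 = 14; lost after week 2, 4.
- Area under change (trapezoids from 0 at day 0): responder 4 + 28 + 75 = 107; lost after week 6, 4 + 28 = 32; lost after week 2, 4.
- Area with last value carried forward: lost after week 6, 4 + 28 + 60 = 92; lost after week 2, 4 + 16 + 24 = 44.
- Time-averaged area: 107/12 = 8.9; 32/6 = 5.3; 4/2 = 2.0.

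| Definition | Responder, complete | Same, lost after wk 6 | Same, lost after wk 2 | Intermediate, complete | Non-responder, complete |
|---|---|---|---|---|---|
| Sum over attended visits | 29 | 14 | 4 | 17.4 | 6 |
| Area over attended visits | 107 | 32 | 4 | 64.2 | 22 |
| Area, last value carried forward | 107 | 92 | 44 | 64.2 | 22 |
| Time-averaged area | 8.9 | 5.3 | 2.0 | 5.35 | 1.8 |
| Completers only | 29 (sum) | excluded | excluded | 17.4 | 6 |

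With an unadjusted sum or area, the responder lost after week 6 falls below the completing intermediate responder, and the one lost after week 2 falls below the completing non-responder. Carrying the last value forward keeps the first above intermediate and puts the second between intermediate and non-responder. Completer-only scoring gives no false low score but reduces the sample.

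Baseline severity: with the responder's percentage falls and an assumed baseline of 10 instead of 20, the absolute sum is 10 × (0.20 + 0.50 + 0.75) = 14.5, half of 29.

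**2. The power figure**

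The stated >95% cannot be reproduced, because it has no effect size, standard deviation or named test. The check therefore works backwards: find the effect that gives exactly 95% power at n = 50, hold it fixed and lower n.

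For a two-sided correlation test at 0.05 (Fisher z), r = tanh[(1.960 + 1.645)/√(n − 3)]:

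- n = 50: tanh(3.605/√47) = 0.482
- n = 45: tanh(3.605/√42) = 0.505
- n = 40: tanh(3.605/√37) = 0.532

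Power at a given r is Φ[atanh(r)·√(n − 3) − 1.960]. The values 45, 40 and 35 correspond to assumed losses of 10%, 20% and 30%. The documents give no rate.

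| Effect held fixed | n = 50 | 45 | 40 | 35 |
|---|---|---|---|---|
| r = 0.482 | 95.0% | 92.6% | 89.2% | 84.5% |
| r = 0.4 | 82.8% | 78.4% | 73.1% | 66.9% |
| r = 0.5 | 96.5% | 94.5% | 91.6% | 87.4% |
| r = 0.6 | 99.7% | 99.4% | 98.8% | 97.5% |

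A regression F test is closer to the plan's linear model. It uses noncentrality n·f², residual degrees of freedom n − p − 1 and R² = f²/(1 + f²). For one term among three predictors, 95% at n = 50 needs f² = 0.271 (partial R² = 0.21), and power is then 92.7%, 89.3% and 84.7% at 45, 40 and 35. For all three terms jointly it needs f² = 0.374 (R² = 0.27), and power is 92.2%, 88.2% and 82.4%. The choice of test changes the picture by about two points at most; the unstated effect size changes it far more.

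**The case against.** A reader might infer that the plan scores early dropouts as poor responders. The documents do not support that. They give no formula, and nothing says that an early leaver's score is summed over attended visits. The effect is marked for an unadjusted sum or area while PASI is still falling, weaker with carry-forward, and absent if incomplete patients are excluded. Even on the simple sum, the responder lost after week 6 (14) lies nearer the intermediate responder (17.4) than the non-responder (6). Nor does the plan say that its responder classes come from the cumulative score; it speaks only of improvement in PASI.

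A reader might also infer that the true power is below 95%. That is not shown either. The plan says more than 95%, and starting from exactly 95% guarantees a fall as n drops. If the true r is 0.6, a 30% loss still leaves 97.5%; if it is 0.4, power is 82.8% with no loss at all. The RNA condition sets a quality standard without a failure rate, and for part (1) it bears only on the baseline lesional sample.

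These objections stand, and they limit the point to what is undefined. They do not remove it: each available reading of the score carries a cost that the plan does not acknowledge, and the power statement cannot be checked by anyone.

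A mixed model is also no complete cure. It relies on data being missing at random, so dropout driven by unobserved worsening could still bias it. It also gives up the planned protection against outlying scores, which is why the robust regression should be kept as a sensitivity analysis.

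**Conclusion.** The point holds in two parts.

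- **Score.** The part (1) outcome is undefined for a patient with a missed visit and unadjusted for baseline PASI. Depending on the rule adopted later, an early-leaving responder scores anywhere from close to a completer (92 against 107) to below a completing non-responder (4 against 22), or is dropped. These sizes rest on the assumed PASI courses. The direction of any bias in the signal associations depends on who leaves and cannot be predicted from the documents.
- **Power.** The >95% is unverifiable, not disproved. If it means exactly 95% for a two-sided correlation at 50, losses of 10% to 30% would take it to between 92.6% and 84.5%. Those loss rates are assumptions.

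Neither part invalidates the trial. Both can be put right before analysis with data the trial already collects.

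**What to change.** 1. **Main part (1) analysis.** Use a longitudinal mixed model of PASI at weeks 2, 6 and 12, with baseline PASI, visit, baseline TNF, baseline IFN, the TNF-by-IFN interaction and signal-by-visit terms. Include all observed visits of every treated patient with a usable baseline lesional RNA sample. State the missing-at-random assumption.
2. **Sensitivity analysis.** Keep the robust regression in completers on a cumulative score whose formula and scale are written down beforehand.
3. **Missed visits elsewhere.** Give a rule for the responder classes, the cross-validated prediction, the repeated measures analysis in part (2) and the repeat using physician global assessment.
4. **Power.** Name the test and restate power as the detectable effect at the expected evaluable number, giving the assumed losses. The correlation values 0.48, 0.51 and 0.53 at 50, 45 and 40 are a guide only. They belong to a single-score test and do not carry over to the mixed model, where a patient who leaves early still contributes the visits attended.

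The cost is modest extra analysis work, reliance on missing at random and a less favourable power statement. No additional patients, visits or assays are needed.

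### Analysis (2) tests whether signal change differs by response only through response classes, although the plan already computes a continuous PASI change score

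*Combined protocol and SAP*

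**What the plan says.** All of this is in Analysis/Statistics.

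- Analysis (1) calculates a cumulative PASI change score for each patient. "This score will then be treated as a continuous response variable", in a robust linear model on the two baseline signals and their interaction.
- It then adds that "we will also categorize patients according to improvement in PASI score (i.e., responders, intermediate-responders, and non-responders"). The expectation is that it will be "possible to unambiguously classify 30% of patients as non-responders, with an equal percentage showing clear improvement in PASI score", with the rest intermediate. With 50 patients that is 15/20/15. No PASI cut-offs are given.
- In analysis (1) the classes serve to "use cross-validation to calculate AUC statistics to directly quantify the capacity of baseline" signals, and the plan also wants "to better characterize quantitative thresholds associated with response and non-response".
- Analysis (2) takes each signal as the response in a repeated measures analysis of variance. Whether its course differs by response is tested in follow-up models "by evaluating interaction effects involving time and 0-1 covariates denoting PASI response patterns". No version with the continuous PASI score is described. The PASI analyses are to be repeated with PGA.
- On power: "With 50 patients recruited and treated, we estimate that we will have >95% statistical power to detect significant effects in the proposed design", at a type I error rate of 0.05. No effect size accompanies this.

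**The concern.** The question in analysis (2), whether etanercept lowers the TNF signal more in patients who improve and leaves IFN high in those who do not, is tested nowhere else in the plan. Cutting improvement into three groups discards its ordering within each group and doubles the numerator degrees of freedom. If signal change tracks improvement in a graded way, both features cost power at a fixed sample of 50. A missed interaction could then be read as evidence against the proposed mechanism, when the continuous score needed to avoid much of that loss is already being calculated.

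**Working it through.** **The plan's own figure.** The >95% power cannot be reproduced, because no effect size or signal standard deviation is given. What follows compares two tests under stated assumptions.

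**Inputs from the documents.** n = 50; alpha 0.05; classes 30/40/30%, so 15/20/15; four measurement times (day 0, weeks 2, 6 and 12, under aim 1).

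**Assumptions.** Let y be improvement in standard normal units. Signal = subject effect + visit effect + g·y·s(t) + e, with s = (0, 1/6, 1/2, 1), proportional to weeks 0/2/6/12, and independent residuals of variance 1. Let r be the correlation between y and the baseline-to-week-12 change in signal. That change has variance g² + 2, so g² = 2r²/(1 − r²). At r = 0.3/0.4/0.5, g² = 0.198/0.381/0.667.

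**Degrees of freedom.**
- Class × visit: (3 − 1)(4 − 1) = 6; error 3 × (50 − 3) = 141.
- Score × visit: 1 × 3 = 3; error 3 × (50 − 2) = 144.

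**Noncentral-F approximation.**
- Σ(s − mean)² = 1.2778 − 4 × 0.4167² = 0.5833.
- Continuous score: λ = 50 × g² × 0.5833 = 5.77/11.11/19.44.
- Share of a normal score kept by a 30/40/30 split: 2 × φ(z₀.₃₀)²/0.3 = 2 × 0.3477²/0.3 = 0.806. Class λ = 0.806 × the above = 4.65/8.96/15.67.
- Power: continuous 49/80/97%; class 30/56/84%.

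**Simulation of the same model.** Size at r = 0 is 4.9% (continuous) and 5.3% (class).

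| Test, graded relation | r = 0.3 | r = 0.4 | r = 0.5 |
|---|---|---|---|
| Continuous score × visit, 3 df | 47% | 78% | 95% |
| Three classes × visit, 6 df | 28% | 54% | 80% |
| Loss (points) | 19 | 24 | 15 |

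The continuous test reaches 95% at r of about 0.50 and the class test at about 0.59. With 80 patients the class test has 48/79/96%, roughly what 50 patients give with the continuous score.

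**How far this depends on the set-up.**
- Other time shapes (continuous v class): linear by visit 47/73/94% v 27/51/78%; full change by week 2, 59/87/98% v 38/66/90%.
- Time as a linear covariate: 64/88/98% v 42/70/91%.
- One responder dummy instead of three classes: about 50% at r = 0.4.
- Ordered-trend coding of the classes: the loss is about 11 points at r = 0.4.
- Left-skewed score used untransformed: 39/69/90%, so the gain over classes is only 10 to 15 points. Normal scores restore 47/77/95%.
- Larger r: once the class test reaches 95% (r of about 0.59), at most 5 points can be lost.

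**Where the classes are as good or better.**
- Signal change proportional to class: continuous 40/69/92%, class 37/67/92%, about equal.
- A step exactly at a class boundary, r = 0.4: continuous 52%, three classes 68%, one matching dummy 80%.
- A steep but smooth rise at that boundary, r = 0.4: continuous 72%, three classes 60%, one dummy 69%. This depends on the steepness chosen.

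**The case against.** The strongest objection is that the plan expects class-shaped behaviour. The rationale describes a subgroup with little or no response and notes that the share of patients with an enriched IFN signature (35-40%) resembles the share with limited response. Analysis (2) expects greater attenuation of TNF "signals in responders compared to intermediate-responders or non-responders". The list of profiles is given as examples, so a single dummy matched to that contrast is permitted. If change really is a step at the cut-off, the continuous test loses about 28 points to that dummy at r = 0.4 (80 − 52). This stands, and it is why the class test should stay. It requires the jump to fall exactly at the cut-off, however, and the plan does not say where the cut-offs lie.

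It is also fair to say that the main association test is already continuous, that the class-by-time models are labelled follow-up, and that no r appears in the documents. All three limit the size of the point without removing it.

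A reader might infer that the cross-validated AUC suffers the same power loss. The documents do not support that. No test on the AUC is planned, no contrast between classes is named, and the AUC is meant to describe discrimination of response status and to inform thresholds. Those uses need classes and give a reason for having them. A concordance index with the continuous score would estimate something else.

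**Conclusion.** The point holds for analysis (2) only. Its test of whether signal change differs by response relies solely on classes. With 50 patients and an assumed graded normal relation, this costs about 15 to 24 points of power over r = 0.3 to 0.5. The loss is about 11 points at r = 0.4 with trend coding and 10 to 15 points against a skewed untransformed score. It shrinks at larger r and reverses under a sharp step at a class boundary. The r values, the time shape and the independent residuals are assumptions of this check.

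Two stronger readings should be resisted. The first is that the plan as a whole categorises its outcome: it does not, since the robust linear model in analysis (1) uses the continuous score. The second is that the >95% power claim is shown to be wrong: without an effect size it can be neither confirmed nor refuted. This is a worthwhile, inexpensive improvement to a supporting analysis.

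**What to change.** In analysis (2):

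1. Make PASI improvement score × time the lead follow-up test, with the score entered as ranks or normal scores so that skewness does not erode the gain.
2. Treat PGA in the same way, as an ordinal score.
3. Keep three-class × time as a prespecified secondary test, with the cut-offs and the classification visit written down before signatures are linked to PASI.

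In analysis (1), keep the cross-validated AUC for response status and thresholds. A concordance index between predicted and observed continuous improvement may be reported beside it as an option, without any claim that the AUC loses power.

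The cost is a few lines of text and no extra patients, samples or visits. The downside is lower power in the lead test if response is truly a sharp step at a class boundary; the retained class test covers that case.

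### Part (2) relies on an uncorrected univariate repeated-measures ANOVA, so the 0.05 error rate of its time and time-by-response tests is not assured; one sentence in the plan would secure it

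*Combined protocol and SAP*

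**What the plan says.** Part (2) of Analysis/Statistics takes the TNF or IFN signal as the response in "a univariate repeated measures analysis of variance, with subject and time as covariates". Two tests are read from this model:

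- **Time effect.** A shift in signal during "treatment will be indicated by a significant time effect".
- **Time-by-response interaction.** Whether shifts differ by clinical response is judged "by evaluating interaction effects involving time and 0-1 covariates denoting PASI response patterns".

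The same part ends with the sample size and error rate: "With 50 patients recruited and treated", "we estimate that we will have >95% statistical power to detect significant effects in the proposed design", at a "Type I error rate of 0.05".

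Lesional biopsies are scheduled at day 0 and weeks 2, 6 and 12 (item 1 under Proposed experiments, and the visit flow chart). The plan names no covariance structure, sphericity check, degrees-of-freedom correction, mixed model or multivariate alternative.

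**The concern.** A univariate repeated-measures ANOVA with a subject effect uses one pooled residual for all within-patient comparisons. Its F tests have the stated level only under sphericity. Two features of this study make that doubtful:

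- Biopsies taken further apart may be less alike than biopsies taken close together.
- Patients may differ in how far the signal moves on treatment. The subject term removes differences in level but not differences in change. Part (2) itself expects stronger TNF attenuation in responders and a persistently high IFN signal in non-responders.

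When sphericity fails, the uncorrected omnibus F test rejects too often. Both tests of part (2), for both signals, depend on this error term, so the risk is a false claim that a signal shifted, or that it shifted differently by response.

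**Working it through.** **Inputs from the plan.** 50 patients; four visits at weeks 0, 2, 6 and 12; level 0.05. Part (1) expects 30% non-responders, 30% clear responders and the rest intermediate, which gives 15, 15 and 20 patients. Dropout is not stated, so complete data are assumed.

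**Inputs that are assumptions.** All covariance structures, because the documents give none.

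**Degrees of freedom.** Time: 4 − 1 = 3 and 3 × 49 = 147, critical F 2.666. Interaction: 3 × 2 = 6 and 3 × (50 − 3) = 141, critical F 2.163.

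**The plan's own figures.** The 0.05 level is reproduced under compound symmetry (first row of the table). The power figure cannot be reproduced, because no effect size, standard deviation, correlation or named test accompanies it. Nothing below depends on it.

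**Measure of departure.** Let λ1, λ2, λ3 be the non-zero eigenvalues of the visit covariance after centring on each patient's mean. Then ε = (Σλ)² / (3 Σλ²), which runs from 1 (sphericity) down to 1/3. The uncorrected F behaves roughly as if both its degrees of freedom were multiplied by ε.

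Two cases can be done by hand, with residual variance 1 and s the SD of individual change in residual SDs:

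- *Patient-specific slopes, s = SD of 12-week change.* Weeks 0, 2, 6 and 12 deviate from their mean of 5 by −5, −3, 1 and 7, with sum of squares 84. So λ = (1 + s² × 84/144, 1, 1). For s = 1: 3.583² / (3 × 4.507) = 0.95. For s = 2: 5.333² / (3 × 13.111) = 0.72. For s = 3: 8.25² / (3 × 41.063) = 0.55.
- *Patient-specific on-treatment shift, the same at weeks 2, 6 and 12.* The centred pattern is (−0.75, 0.25, 0.25, 0.25), with sum of squares 0.75. So λ = (1 + 0.75 s², 1, 1). For s = 2: 6² / (3 × 18) = 0.67. For s = 3: 9.75² / (3 × 62.063) = 0.51.

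**Simulated error with no true effect, nominal 0.05, no correction.** There were 40,000 trials per row (simulation error about 0.001), except rows marked †, which had 20,000.

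| Assumed covariance | ε | Time | Interaction |
|---|---|---|---|
| Compound symmetry, correlation 0.5 | 1.00 | 0.051 | 0.050 |
| Compound symmetry, level variance 9 × residual | 1.00 | 0.050 | 0.050 |
| Correlation 0.60 per week apart | 0.95 | 0.053 | 0.054 |
| Correlation 0.80 per week | 0.83 | 0.056 | 0.062 |
| Correlation 0.90 per week | 0.73 | 0.064 | 0.072 |
| Correlation 0.95 per week | 0.66 | 0.071 | 0.077 |
| Equally spaced visits, 0.7 between neighbours | 0.77 | 0.062 | 0.067 |
| Slopes, s = 0.25 to 0.5 | 1.00 | 0.047–0.050 | 0.049–0.050 |
| Slopes, s = 1 | 0.95 | 0.050 | 0.053 |
| Slopes, s = 2 | 0.72 | 0.068 | 0.071 |
| Slopes, s = 3 † | 0.55 | 0.079 | 0.092 |
| Visit SDs differing twofold | 0.84 | 0.057–0.060 | 0.062–0.063 |
| On-treatment shift, s = 2 † | 0.67 | 0.070 | 0.079 |
| On-treatment shift, s = 3 † | 0.51 | 0.085 | 0.098 |

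**Ceiling.** At ε = 1/3, the time test's critical value 2.666 referred to F(1, 49) gives 0.109. The interaction's 2.163 referred to F(2, 47) gives (1 + 2 × 2.163/47)^(−23.5) = 0.126.

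**With Greenhouse-Geisser.** Across all the simulations, the error of both tests lay between 0.044 and 0.054.

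**The case against.** The strongest reply is that the documents do not show the assumption failing, and that several stronger readings do not hold.

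- **A reader might infer that the unequal visit gaps break the assumption.** They do not. With these same visits, compound symmetry gives about 5%, and decaying correlation inflates the error with equal spacing too (0.062 and 0.067).
- **A reader might cite the large patient-to-patient variation described under Rationale and Hypothesis.** That is variation in signal level, which the subject term absorbs. The second row of the table shows no inflation.
- **A reader might treat the expected differences between response classes as the cause.** In the interaction model those differences are the effect under test, so only differences in change within a class matter, and the documents are silent on them. In the time model, which has no response term, class differences do enter the residual. They can produce a false positive only if average change is zero.
- **A reader might conclude that 0.05 is exceeded.** With no covariance in the documents, the supported statement is that it is not assured. Several plausible cases show little or no inflation.
- **A reader might extend the point to comparisons between pairs of visits.** A pooled error can be badly wrong there, but the plan specifies no such comparisons.
- **A reader might take time to be a numeric term in weeks.** The plan calls both subject and time covariates, so the word is used loosely and does not settle the coding.

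All of these limits stand. They do not answer the remaining point: the plan names a particular test, ties it to a 0.05 error rate, and says nothing about the condition on which that rate depends.

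**Conclusion.** The concern holds in a limited form. The 0.05 level of the time and time-by-response tests in part (2) is not assured, because the named analysis needs sphericity and no safeguard is stated. The plausible range is from about 5% to about 7–8%. About 8% (time) and 10% (interaction) arise only if the SD of individual change is around three times the residual SD. These figures rest on assumed covariances, normal data, complete follow-up and classes of 15, 20 and 15.

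It would be wrong to infer that the trial's main question is compromised. Part (1) uses one cumulative score per patient in a robust linear model, plus cross-validated AUC, and neither uses this error term. This is a cheap improvement to a supporting analysis.

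**What to change.** In part (2), state that visit enters as a four-level factor, and choose one of the following for all within-patient tests:

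- keep the repeated-measures ANOVA and apply the Greenhouse-Geisser correction; or
- use a mixed model for repeated measures with unstructured within-patient covariance and Kenward-Roger degrees of freedom.

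Either is adequate for the error rate. The mixed model also retains patients with a missing sample, which may be useful because item 1 under Proposed experiments accepts only high-quality RNA. If any comparisons between individual visits are reported, use an error term specific to each contrast rather than the pooled residual.

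The cost is a sentence or two in the plan and standard software, with slightly fewer effective degrees of freedom and slightly larger p-values. No patients, samples or visits are added. The effect on power cannot be calculated because the plan gives no effect size.
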